10.5.3 Mean Change in Mean Daily Dose of Iron Chelation Therapy

For the primary CSR, the ICT mean daily dose summary has been provided for subjects who did not change ICT drug from baseline to post-baseline and only one ICT drug has been used. Descriptive statistics for mean daily dose have been summarized at baseline and the post-baseline visit for each ICT drug. The baseline mean daily dose has been calculated using the ICT dosage during the 12 weeks on or prior to first study drug treatment. and the post-baseline mean daily dose was calculated during the last 12 weeks of the 48-week double-blind treatment period or the last 12 weeks of the study treatment for early discontinued subjects.

For the final CSR, the post-baseline mean daily dose will be calculated during the last 24 weeks on or prior to Week 48, Week 96, Week 144, Week 192, *etc.* if the assessments are on or before the efficacy cutoff date. If some or all of the ICT doses occur after the efficacy cutoff, the ICT doses will not be included in the reported interval. The overall post-baseline ICT mean daily dose calculated by the last 24-week prior to the efficacy cutoff date will also be conducted. The definition of baseline mean daily dose remains the same as in the primary CSR.

The same descriptive statistic summary for baseline and post-baseline ICT drug mean daily dose was provided for subjects in each baseline liver iron content category (≤ 3 mg/gr dry weight and > 3 mg/gr dry weight).

The change from baseline in mean daily dose at Week 48, Week 96, and overall post-baselines will be analyzed using an ANCOVA model with the geographical regions defined at randomization and baseline ICT mean daily dose as covariates for the ITT population for subjects who did not change ICT drug from baseline to post-baseline and only one ICT drug has been used.

A summary showing the number and percentage of subjects who took monotherapy (i.e., only one ICT drug) vs. combo therapy (i.e., more than one ICT drug) at the 12-week baseline period and 24-week post-baseline period at Week 48, Week 96, Week 144, Week 192, *etc.*, and Overall will be provided.

Bar plot was provided for percent of subjects who took each ICT drug at baseline and post-baseline for subjects who did not change ICT drug from baseline to post-baseline and only one ICT drug has been used. A similar bar plot was provided for percent of subjects who took monotherapy or combo therapy at baseline and post-baseline. No bar plots will be provided in the final CSR.

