Iron chelation therapy (ICT) is essential to survival of heavily transfused patients; however, it is frequently associated with adverse events. It has been reported that compliance with the rigorous requirements of daily subcutaneous infusions of deferoxamine (DFO) was a serious limiting factor and that life expectancy for noncompliant patients was not different from that in the pre-DFO era ([Cappellini, 2014](#), [Gabutti, 1996](#)).

Although two oral iron chelators are now available in various regions, deferiprone (DFP) and deferasirox (DFX), some patients do not respond to treatment at maximally tolerated doses ([Guidelines for the Management of Transfusion Dependent Thalassemia, 2014](#)). Reducing transfusion burden will very likely reduce ICT daily dosage requirements and possibly the need for ICT at all, which will provide a number of benefits to the patients.

Quality of Life:

TranQol and Short Form (SF)-36, questionnaires will be used to assess the impact of the treatment on the quality of life in patients with  $\beta$ -thalassemia. SF-36 has been used in several prior studies in the  $\beta$ -thalassemia population and is well known to Investigators from multiple countries. TranQol has been developed for and validated in patients with transfusion-dependent  $\beta$ -thalassemia ([Klaassen, 2014](#)). It contains questions that specifically pertain to QoL issues related to transfusion burden in thalassemia patients, such as impact on school or work activities.

Healthcare Resource Utilization:

The economic objective of this study is to characterize medical resource utilization among subjects treated with luspatercept as compared to subjects receiving placebo treatment. To facilitate this aim, medical healthcare resource utilization (HRU) data will be collected. In addition, the number of transfusion events will be evaluated, as these relate directly to hours or days devoted to receiving RBC transfusions that can impact patients' quality of life.

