### 9.2. Study Population Definitions

Study populations to be analyzed are defined as follow:

**Intent-to-treat (ITT):** The ITT population will consist of all randomized subjects regardless of whether or not the subject received IP. All efficacy analyses will be conducted for the ITT population and will be analyzed based on randomization group.

**Safety:** The safety population will consist of all subjects who were randomized and received at least one dose of IP. Subjects will be included in the treatment group corresponding to the IP they actually received.

Statistical methods to handle missing data will be described in the SAP. The SAP will describe any predefined rules for including/excluding any subjects with data from any analyses (eg, time windows, visit by visit analysis, endpoint analysis, protocol violation).

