##### 9.6.3.2. Mean Change in Mean Daily Dose of Iron Chelation Therapy (ICT)

For a subject, the baseline mean daily dose will be calculated using ICT dosage during the 12 weeks prior to first study drug treatment. The post baseline mean daily dose will be calculated using ICT dosage during the last 12 weeks of the 48 weeks double-blind Treatment Period or last

12 weeks of study treatment if discontinued early. The change in daily dose for each subject is calculated as the difference of post-baseline mean daily dose and baseline mean daily dose. ANCOVA will be used to compare the treatment difference between groups, with the stratification factor and baseline ICT value as covariates.

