3.2.2 Extended Secondary Objectives

The following secondary objectives will be conducted in this final CSR:

- To evaluate the mean change from baseline in liver iron concentration (LIC) versus placebo up to final database lock
- To evaluate the mean change from baseline in mean daily dose of iron chelation therapy (ICT) used versus placebo up to final database lock
- To evaluate the mean change from baseline in serum ferritin versus placebo up to final database lock
- To evaluate the effect of luspatercept on osteoporosis/osteopenia, total hip and lumbar spine measured by bone mineral density (BMD) versus placebo up to final database lock
- To evaluate mean change from baseline in myocardial iron versus placebo up to final database lock
- To evaluate the effect of luspatercept on healthcare resource utilization versus placebo up to final database lock
- To evaluate the proportion of subjects who are transfusion independent for ≥ 8 weeks versus placebo up to final database lock

- To evaluate the duration of reduction in transfusion burden or transfusion independence up to final database lock
- To evaluate the time to erythroid response up to final database lock
- To evaluate the post-baseline transfusion events frequency versus placebo up to final database lock
- Evaluate the safety of luspatercept versus placebo up to final database lock.

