5.2 Analysis Populations

5.2.1 Intent-to-Treat Population

The intent-to-treat (ITT) population consists of all randomized subjects regardless of whether or not the subject received IP. All efficacy analyses will be conducted for the ITT population and will be analyzed based on randomization group.

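### The iron-chelation dose ANCOVA is labelled ITT but limited to subjects on one unchanged chelator, a subset partly defined after randomisation, and the handling of subjects who stop chelation is not stated

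*SAP*

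**What the plan says.** - **Objective.** SAP 3.2.2: "To evaluate the mean change from baseline in mean daily dose of iron chelation therapy (ICT) used versus placebo up to final database lock". Protocol Table 1 has the same objective. Neither names a subset.
- **Protocol analysis.** Protocol 9.6.3.2: "The change in daily dose for each subject is calculated as the difference of post-baseline mean daily dose and baseline mean daily dose", and "ANCOVA will be used to compare the treatment difference between groups, with the stratification factor and baseline ICT value as covariates". It sets no condition on which chelator is taken.
- **SAP analysis.** SAP 10.5.3 plans the ANCOVA at Week 48, at Week 96 and overall, adjusted for region and baseline dose. It is to be run "for the ITT population for subjects who did not change ICT drug from baseline to post-baseline and only one ICT drug has been used". Each post-baseline mean covers a 24-week window. The primary report had a similar limit: "the ICT mean daily dose summary has been provided for subjects who did not change ICT drug from baseline to post-baseline", again with a single drug only.
- **Population.** Protocol 9.2: "The ITT population will consist of all randomized subjects regardless of whether or not the subject received IP". SAP 5.2.1: "All efficacy analyses will be conducted for the ITT population and will be analyzed based on randomization group".
- **Other ICT output.** SAP 10.5.3 adds a table of single-drug versus combination therapy by period. It names no category for subjects on no chelator. The missing-data rules in SAP 10.7 cover RBC units and liver iron only.
- **Expected effect.** Protocol 1.3.2.2 (Iron Chelation Therapy Use) says that a lower transfusion burden "will very likely reduce ICT daily dosage requirements and possibly the need for ICT at all".

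**The concern.** The endpoint is the change in chelator dose, and entry to the analysis depends partly on what happens to chelation after randomisation. The protocol expects treatment to influence exactly that. If switching, adding a drug or stopping differs by arm, the two groups left in the ANCOVA are no longer the randomised groups, and the ITT label hides this.

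For stopping, the direction of the bias is clear. A subject who no longer takes a chelator has the largest possible reduction. If more luspatercept subjects stop and are left out, the benefit is understated. For switches and added drugs the direction cannot be known in advance.

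The SAP plans no other test of this objective. The ANCOVA is also stated once, with no term for drug, so it appears to pool mg doses of different chelators.

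**Working it through.** **The plan's own figure.** The documents give no sample size, dose variance or stopping rate for the ICT endpoint. Their one sample-size figure, N = 300 for the primary endpoint (40% versus 20%, 2:1, 90% power), reproduces with a continuity-corrected two-proportion formula: 90 + 180 = 270, and 270 / 0.9 = 300. It has no bearing on this point.

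**Step 1. Who is in the restricted ANCOVA under SAP 10.5.3?**

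| Chelation course | Included? | Basis |
|---|---|---|
| One drug, same drug, dose changed | Yes | Rule as written |
| One drug, stopped during the window | Yes | One unchanged drug; counting of drug-free days not stated |
| One drug, stopped before the window | Probably not | Not stated; there is no post-baseline drug to compare, and no rule assigns 0 |
| Switched to another drug | No | Drug changed |
| Second drug added | No | More than one drug |
| Two drugs at baseline, including step-down to one | No | More than one drug; already fixed by baseline status |

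The switch, added-drug and stopped rows depend on events after randomisation. The last row does not, but it takes step-down out of the test.

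**Step 2. What would leaving out stoppers do?** This is an illustration, and all rates are assumptions. Work in percent of baseline dose. Let s be the share who stop (post-baseline dose 0, a change of −100) and m the mean change among those who continue.

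- All-subject mean change per arm: A = (1 − s) × m + s × (−100)
- All-subject difference: A(luspatercept) − A(placebo)
- Restricted difference: m(luspatercept) − m(placebo)

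Placebo continuers are held at m = 0. Luspatercept continuers are given m = 0 or m = −10.

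| Stop, luspatercept / placebo | m = 0: restricted | m = 0: all | m = −10: restricted | m = −10: all |
|---|---|---|---|---|
| 2% / 1% | 0 | −1.0 | −10 | −10.8 |
| 5% / 1% | 0 | −4.0 | −10 | −13.5 |
| 10% / 2% | 0 | −8.0 | −10 | −17.0 |
| 20% / 2% | 0 | −18.0 | −10 | −26.0 |
| 5% / 5% | 0 | 0.0 | −10 | −9.5 |

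Example, 10% / 2% with m = −10: luspatercept 0.90 × (−10) − 10 = −19; placebo 0.98 × 0 − 2 = −2; difference −17, against −10 in the restricted analysis.

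With unequal stopping, the understatement runs from 0.8 (2% / 1%, m = −10) to 18 points (20% / 2%, m = 0). With equal stopping, the gap is 0 to 0.5 points, and the 0.5 is in the opposite direction.

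**Step 3. Precision.** If a share e of subjects is excluded at the same SD, the standard error grows by 1/√(1 − e): 1.05 at e = 10% and 1.41 at e = 50%.

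**The case against.** **The SAP may set inclusion rules.** Protocol 9.2 says the SAP will define them, and mg doses of different chelators may not be comparable, which is a plausible reason to leave out switchers. The SAP does not give that reason. It would not justify the ITT label, and it does not apply to stoppers, whose dose is 0 on any scale. An ANCOVA with no term for drug would pool chelators anyway.

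**Part of the restriction is not post-randomisation.** Leaving out subjects on combination therapy at baseline narrows the population without breaking the randomised comparison. This stands.

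**Changes may be few.** Protocol 8.1.3 ties ICT use to the label and to investigator practice before randomisation. This may hold down the number of changes, but it rules none out, and exclusion criterion 13 allows chelation to be started during treatment.

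**Other output shows part of the picture.** SAP 8.7 lists all chelation therapies. Tables carry the population size (SAP 5.1), so subjects on no chelator might be found by subtraction if that is the denominator. Neither gives a comparison by arm.

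**Stopping is not always a benefit.** Protocol 1.3.2.2 notes that adverse events with ICT are frequent, so a 0 for someone who stopped for intolerance would count as a maximal gain. This stands, and it is why the fix asks for reasons and does not replace the main analysis.

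**The consequence is limited.** The endpoint lies outside the gate-kept tests (Protocol 9.6.2, SAP 10.1), and this SAP serves the final report after unblinding. This stands.

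**Conclusion.** The ICT ANCOVA is not an ITT analysis. It is run in a subset partly defined after randomisation and narrower than Protocol 9.6.3.2, and it is the only test of this secondary objective in the SAP. If chelation changes differ by arm, it is biased. If more luspatercept subjects stop and are left out, it understates the reduction by about 1 to 18 percentage points of baseline dose under the assumed rates (2% to 20% versus 1% to 2%), and by almost nothing if stopping is equal. The true size is unknown because the documents give no stopping rates.

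A reader might infer three stronger things, none of which the documents support:

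- **That everyone who stops is removed.** Exclusion of those who stop before the window is the likelier reading, but the wording could also keep them at dose 0, and those who stop within the window stay in.
- **That the analysis cannot detect the effect the protocol expects.** The protocol calls a lower dose very likely and no need for ICT only possible. Reductions on the same single drug are measured.
- **That the analysis would report no effect.** A restricted difference of 0 arises only if the continuers' mean change is the same in both arms.

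This should be corrected before the final analysis, but no confirmatory conclusion depends on it.

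**What to change.** 1. Name the analysis set for what it is, not ITT, and report the number excluded by arm and reason.
2. State that a subject on one drug at baseline who stops chelation enters with dose 0 for days without ICT while under follow-up. Report reasons for stopping where recorded, since stopping for intolerance is not a benefit.
3. Add a no-ICT category to the table of single-drug versus combination therapy.
4. Add a comparison by arm (CMH stratified by region) of the proportion of baseline ICT users who stopped ICT or stepped down from combination to single-drug therapy, labelled as added after unblinding.
5. Present the restricted dose analysis by drug, or adjust it for drug, and treat it as supportive.

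An analysis of all baseline ICT users, with dose as a percentage of the subject's own baseline, may be added as a sensitivity analysis. It should not replace the planned one, because its handling of switches and added drugs is debatable.

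**Cost.** SAP wording, a small amount of programming and a stated convention for drug switches. Chelator type, dates and dose changes are already recorded (Protocol 6.1 and 6.2).

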10.5.4 Mean Change in Serum Ferritin Level

In the primary CSR, descriptive statistics for serum ferritin level have been summarized at baseline and the post-baseline visit, where the baseline mean serum ferritin was measured during the 12 weeks prior to the first dose and the post-baseline mean serum ferritin was calculated during the last 12 weeks of the 48- week double-blind treatment period or the last 12 weeks of the study treatment for early discontinued subjects. Change from baseline has been summarized at the post-baseline visit.

For the final CSR, the post-baseline will be calculated as the mean of serum ferritin values during the last 24 weeks on or prior to Week 48, Week 96, Week 144 , Week 192, *etc.* if the assessments are on or before the efficacy cutoff date. If the assessments occur after the efficacy cutoff, the assessments will not be included in the reported interval. The overall post-baseline serum ferritin calculated by the mean of last 24-week serum ferritin prior to the efficacy cutoff date will also be conducted. The definition of baseline mean serum ferritin remains the same as in the primary CSR. The descriptive statistics will be summarized at each post-baseline time point.

The change from baseline in serum ferritin at the Week 48, Week 96, and overall post-baselines will be analyzed using an ANCOVA model with the geographical regions defined at randomization and baseline serum ferritin value as covariates for the ITT population.

All the serum ferritin data will be presented in a listing.

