#### **9.6.3.3. Mean Change in Serum Ferritin Level**

For a subject, the baseline mean serum ferritin will be calculated during the 12 weeks prior to first study drug treatment. The post baseline mean serum ferritin will be calculated during the last 12 weeks of the 48 weeks double-blind Treatment Period or last 12 weeks of study treatment if discontinued early. The change is calculated as the difference of post-baseline mean serum ferritin and baseline mean serum ferritin. ANCOVA will be used to compare the treatment difference between groups, with the stratification factors and baseline serum ferritin value as covariates.

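### For serum ferritin and chelation dose, the final SAP replaces the protocol's 12-week window at Week 48 with a 24-week one, after unblinding and without a stated reason, and tests the arms on it

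*SAP*

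**What the plan says.** **Protocol.** For ferritin (9.6.3.3): "The post baseline mean serum ferritin will be calculated during the last 12 weeks of the 48 weeks double-blind Treatment Period", or over the last 12 weeks of treatment for a subject who stops early. For chelation (9.6.3.2): "The post baseline mean daily dose will be calculated using ICT dosage during the last 12 weeks of the 48 weeks double-blind Treatment Period", with the same rule for early discontinuers. Table 2 gives the same post-baseline timeframe for both. Each is compared between arms; for ferritin, "ANCOVA will be used to compare the treatment difference between groups, with the stratification factors and baseline serum ferritin value as covariates".

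**SAP, primary report.** SAP 10.5.3 and 10.5.4 report that the protocol's window was used, for example "the post-baseline mean serum ferritin was calculated during the last 12 weeks of the 48- week double-blind treatment period", again with the early-discontinuer rule.

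**SAP, final report.** For ferritin, "the post-baseline will be calculated as the mean of serum ferritin values during the last 24 weeks on or prior to Week 48", and likewise at later timepoints. For chelation, "the post-baseline mean daily dose will be calculated during the last 24 weeks on or prior to Week 48". Only values up to the efficacy cutoff count, and baseline stays at 12 weeks. Then: "The change from baseline in serum ferritin at the Week 48, Week 96, and overall post-baselines will be analyzed using an ANCOVA model"; chelation dose gets the same model. SAP 10.5 attaches a least-squares mean difference, a 95% confidence interval and a p-value to every ANCOVA.

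**Timing.** SAP 15.1 places the primary database lock and unblinding after every subject had completed or stopped the 48-week period. SAP Section 2 gives 11 May 2018 as the data cutoff, and says analyses of data before that date are carried into the final report without being updated. The signature page of this SAP is dated 11-12 March 2021.

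**The concern.** Week 48 closes the 48-week period for which the protocol defined these comparisons, and its data were complete when the study was unblinded. A new Week 48 model in the final report therefore adds no information on that period. It changes which weeks are averaged and which subjects have a value. SAP 10.5.3 and 10.5.4 neither explain the change nor flag it as a departure from the protocol, and it sits badly with the SAP's own rule that earlier analyses are not updated.

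What is at stake is how the Week 48 iron results are read. If the protocol's ANCOVA was run for the primary report, the trial will carry two Week 48 estimates and p-values for each endpoint, one of them defined once allocation was known. If it was not run, the only Week 48 test will use a window that the protocol does not contain.

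**Working it through.** The plan gives no power figure, expected difference or time course for either endpoint, so it has no figure of its own to reproduce. The check compares the two windows. SAP 5.1 gives day limits for transfusion endpoints only; I assume that the same limits apply here.

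**1. Overlap.** Weeks 37-48 are Days 254-337, so 337 − 254 + 1 = 84 days. Weeks 25-48 are Days 170-337, so 337 − 170 + 1 = 168 days. The share of the new window outside the protocol's is (168 − 84)/168 = 50%.

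**2. Scheduled ferritin samples.** Protocol Table 3 schedules ferritin before each dose in the Treatment Period, every 21 days, on Day 1 + 21k if there are no delays.
- 12-week window: Days 274, 295, 316, 337 (4 samples).
- 24-week window: those four plus Days 190, 211, 232, 253 (8 samples).

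**3. Effect on the arm difference.** Let g(d) be the arm difference on Day d as a fraction of its final value. The ratio is the mean of g over the 8 days divided by its mean over the 4 days. All the time courses are assumptions.

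| Assumed course | g(d) | 12-week mean | 24-week mean | Ratio | Shrinkage |
|---|---|---|---|---|---|
| Plateau by Week 24 | 1 | 1.000 | 1.000 | 1.00 | 0% |
| Linear to plateau at Week 36 | min(1, (d − 1)/252) | 1.000 | 0.938 | 0.94 | 6% |
| Linear growth to Week 48 | (d − 1)/336 | 0.906 | 0.781 | 0.86 | 14% |
| Onset at Week 24, then linear | (d − 169)/168 | 0.813 | 0.563 | 0.69 | 31% |

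For example, in the third row the four late values are 0.8125, 0.875, 0.9375 and 1 (mean 0.90625). Adding 0.5625, 0.625, 0.6875 and 0.75 brings the mean to 0.78125, and 0.78125/0.90625 = 0.862.

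Day 337 is the Dose 17 visit, which Table 3 places in the Long-term Treatment Period. Without it, the last two rows become 0.750/0.875 = 0.857 and 0.500/0.750 = 0.667, so 14% and 33%. Chelation dose is recorded continuously, so week midpoints serve instead: (25 + 48)/2 = 36.5 against (37 + 48)/2 = 42.5. Linear growth gives 36.5/42.5 = 0.859, and onset at Week 24 gives 12.5/18.5 = 0.676. The order of size is the same.

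**4. Who has a Week 48 value.** SAP Section 10 sets the final efficacy cutoff at the earliest of death, study discontinuation and last dose + 20 days. If the last dose falls on Day 149 or before, the cutoff is at most 149 + 20 = Day 169, before the new window opens on Day 170. With no delays this covers anyone stopping at or before Dose 8 (Day 148). Such a subject has no final-report Week 48 value, although the protocol and the primary report use that subject's last 12 weeks of treatment. For chelation, the ANCOVA is limited to subjects on one unchanged drug from baseline to post-baseline, so doubling the window can also change who qualifies.

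**The case against.** **These are supportive endpoints.** Both are listed under other efficacy endpoints, outside the ordered testing in Protocol 9.6.2 and SAP 10.1. That stands, and it limits the weight of the point.

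**The protocol-defined result survives.** The SAP sets the two definitions side by side and keeps the primary-report results. This is true, but it does not explain why a second Week 48 comparison is needed or which one governs.

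**There is an ordinary reason for 24 weeks.** After Week 48, Table 3 reduces ferritin to every 4 doses (about every 12 weeks), with none marked at continuing open-label doses. A 12-week window would then hold about one value, and one common window makes a tidier long-term series. This is plausible for later timepoints, although the SAP does not say it. It does not carry back to Week 48, where four samples are scheduled, nor to chelation dose, which is recorded continuously.

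**More samples give more precision.** With a common within-subject correlation ρ (assumed), the variance of the mean of 8 samples relative to 4 is [(1 + 7ρ)/8]/[(1 + 3ρ)/4]: 0.650/0.700 = 0.93 at ρ = 0.6, and 0.9125/0.925 = 0.99 at ρ = 0.9. The gain is small and the net effect on the test is unknown.

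**Early discontinuers are still covered.** The overall post-baseline analysis uses the last 24 weeks before each subject's cutoff, so they count there. That analysis mixes subjects at very different times and does not replace the Week 48 comparison.

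**The 12-week baseline is the same in both arms**, so pairing it with a 24-week mean creates no between-arm bias by itself. That is accepted.

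**Conclusion.** The departure is real. At Week 48 the final SAP changes both the weeks averaged and the subjects who contribute, after unblinding, and tests the arms on the result. The shrinkage of 0% to about 31% rests wholly on assumed time courses; if the effect has levelled off by Week 24, only the analysed set differs. The timing rests on this SAP's account of what each report uses and on its signature dates, since the 2018 SAP is not among the documents.

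A reader might infer more than the documents support:
- **That the window was chosen because of the results.** Timing is shown; motive is not. In every case above the wider window leaves the arm difference unchanged or makes it smaller.
- **That two Week 48 p-values certainly exist.** SAP 10.5.3 and 10.5.4 describe the primary-report results only descriptively. An ANCOVA at that stage is inferred from the protocol and from the completed versus-placebo objectives in SAP 3.2.1.
- **That the trial's error control is damaged.** The primary and key secondary tests are untouched.
- **That the effect could be halved.** This needs all of a chelation difference to appear exactly at Week 36 (12 of 24 weeks against 12 of 12). Nothing in the documents points to that.
- **That the Week 96 tests should go.** Nothing here shows them to be wrong.

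**What to change.** In SAP 10.5.3 and 10.5.4, make the protocol's 12-week window, with its early-discontinuer rule, the only between-arm test at Week 48. Carry over the primary-report result, or run that ANCOVA now if it was not done. Keep the 24-week window for later timepoints, including the Week 96 ANCOVA.

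If a 24-week value at Week 48 is wanted so that the long-term series is on one footing, show it descriptively, label it post hoc, give the reason, and cross-refer to the 12-week result.

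The cost is a few lines of SAP text and one window definition; the sample size and the primary and key secondary tests do not change. The one drawback is that the long-term display would carry two window definitions, so part of any apparent change from Week 48 to Week 96 could come from the window. The descriptive 24-week value, if shown, deals with that.
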